6.3.4 Follow-up for toxicities

An unscheduled visit should be performed in all cases below where toxicity monitoring is recommended more frequently than defined by the schedule of assessments ([Table 7-1](#)).

6.3.4.1 Guidelines for the follow-up of laboratory hematologic abnormalities

In case of any occurrence of febrile neutropenia, neutropenia \geq grade 3 or thrombocytopenia \geq grade 3, tests must be performed weekly (or more frequently if clinically indicated) until the event resolves to \leq grade 2. Subsequent monitoring must be performed every 4 weeks. See [Table 6-4](#).

6.3.4.2 Guidelines for the follow-up of liver laboratory abnormalities

In patients with any clinically relevant laboratory liver abnormality, as defined below, hepatic toxicity monitoring must include **ALL** of the following live function tests (LFTs): albumin, ALT, AST, total bilirubin (fractionated if total bilirubin $> 2.0 \times$ ULN), alkaline phosphatase and GGT).

Note: for patients with Gilbert Syndrome, total and direct bilirubin must be monitored, but intensified monitoring applies to changes in direct bilirubin only.

In case of any occurrence of ALT/AST/total bilirubin increase to grade 2 the LFTs must be monitored weekly (or more frequently if clinically indicated) until the event resolves to \leq grade 1. Thereafter monitoring must be continued every other week (or more frequently if clinically indicated) for two additional cycles (e.g. 8 weeks). If there is no recurrence of grade 2 ALT/AST/total bilirubin elevations during this period, subsequent monitoring must be performed every 4 weeks. For patients with liver metastasis and grade 2 AST/ALT at baseline, increased monitoring is required for grade 3/4 AST/ALT; follow guidelines for grade 3 or 4 AST/ALT.

In case of any occurrence of ALT/AST/ total bilirubin increase to grade 3 or 4, LFTs must be monitored weekly (or more frequently if clinically indicated) until the event resolves to \leq grade 1 (or to baseline). Thereafter monitoring must be continued every other week (or more frequently if clinically indicated) for four additional cycles (e.g. 16 weeks). If there is no recurrence of \geq grade 2 ALT/AST/ total bilirubin elevations during this period, subsequent monitoring must be performed every 4 weeks.

Patients who discontinue study treatment due to liver toxicity must be monitored weekly (or more frequently if clinically indicated) until the event resolves to \leq grade 1 or stabilization occurs (no CTCAE grade change over 4 weeks). Refer to [Table 6-4](#).

Patients with transaminase increase combined with total bilirubin (TBIL) increase may be indicative of potential drug-induced liver injury (DILI), and should be considered as clinically important events.

The threshold for potential DILI may depend on the patient's baseline AST/ALT and TBIL value; patients meeting any of the following criteria will require further follow-up as outlined below:

- For patients with normal ALT and AST and TBIL value at baseline: AST or ALT > 3.0 x ULN combined with TBIL > 2.0 x ULN
- For patients with elevated AST or ALT or TBIL value at baseline: [AST or ALT > 2 x baseline AND > 3.0 x ULN] OR [AST or ALT > 8.0 x ULN], combined with [TBIL > 2 x baseline AND > 2.0 x ULN]
- Medical review needs to ensure that liver test elevations are not caused by cholestasis, defined as: ALP elevation > 2.0 x ULN with R value (ALT/ALP in x ULN) < 2 in patients without bone metastasis, or elevation of ALP liver fraction in patients with bone metastasis.
- Note: (The R value is calculated by dividing the ALT by the ALP, using multiples of the ULN for both values. It denotes the relative pattern of ALT and/or ALP elevation is due to cholestatic or hepatocellular liver injury).
- In the absence of cholestasis, these patients should be immediately discontinued from study drug treatment, and repeat LFT testing as soon as possible, preferably within 48 hours from the awareness of the abnormal results. The evaluation should include laboratory tests, detailed history, physical assessment and the possibility of liver metastasis or new liver lesions, obstructions/compressions, etc.
 - Laboratory tests should include ALT, AST, albumin, creatinine kinase, total bilirubin, direct and indirect bilirubin, GGT, prothrombin time (PT)/INR and alkaline phosphatase.
 - A detailed history, including relevant information, such as review of ethanol, concomitant medications, herbal remedies, supplement consumption, history of any pre-existing liver conditions or risk factors, should be collected.
 - Further testing for acute hepatitis A, B, C or E infection and liver imaging (eg, biliary tract) may be warranted.
 - Blood sample can be collected as close as possible to last dose of study drug in the event that a patient experiences hepatotoxicity, as needed.
 - Additional testing for other hepatotropic viral infection (CMV, EBV or HSV), autoimmune hepatitis or liver biopsy may be considered as clinically indicated or after consultation with specialist/hepatologist.

All cases confirmed on repeat testing meeting the laboratory criteria defined above, with no other alternative cause for LFT abnormalities identified should be considered as “medically significant”, thus, met the definition of SAE ([Section 8.2.1](#)) and reported as SAE using the term “potential drug-induced liver injury”. All events should be followed up with the outcome clearly documented.

6.3.4.3 Guidelines for the follow-up of renal laboratory abnormalities

In case of any occurrence of serum creatinine grade ≥ 2 , tests must be performed weekly (or more frequently if clinically indicated) until the event resolves to \leq grade 1. Subsequent monitoring must be performed every 4 weeks.

In case of any occurrence of serum creatinine \geq grade 3, tests must be performed twice weekly (or more frequently if clinically indicated) until the event resolves to \leq grade 1. Subsequent monitoring must be performed every 4 weeks. See [Table 6-4](#).

6.3.4.4 Guidelines for monitoring pneumonitis

Monitor patients for pulmonary symptoms indicative of pneumonitis. In addition, withhold LDK378 for acute onset of new or progressive unexplained pulmonary symptoms, such as dyspnea, cough and fever and during diagnostic workup for pneumonitis/ILD.

See also dose modification guidelines described in [Table 6-3](#).

6.3.4.5 Guidelines for the treatment of study drug induced nausea and vomiting

Nausea and vomiting are among the most frequently reported AEs following treatment with LDK378 and patients must therefore be closely monitored for the appearance of these AEs.

The investigator should consider/investigate potential concomitant medication, food or comorbidity driven causes of nausea and/or vomiting and remedy these causes if possible (e.g. discontinuation of concomitant medication, dietary modification, treatment of comorbidity).

Individualized supportive and anti-emetic treatment should be initiated, as appropriate, at the first signs and/or symptoms of these AEs. In patients with vomiting, the patient should be monitored for signs of dehydration and instructed to take preventive measures against dehydration.

Concomitant medication for the treatment of nausea and/or vomiting should follow local practice and the investigator's best judgment. For moderate emetogenic drugs, such as LDK378, International Guidelines for anti-emetic treatment recommend early treatment with 5-HT3-receptor antagonists (5-HT3RAs).

Dose adaptation of LDK378 in case of treatment related nausea and/or vomiting must follow the guidelines presented above in [Table 6-3](#).

6.3.4.6 Guidelines for the treatment of study drug induced diarrhea

Diarrhea is among the most frequently reported AEs following treatment with LDK378, and patients must therefore be closely monitored for the appearance of this AE.

The investigator should consider/investigate potential concomitant medication, food or comorbidity driven causes of diarrhea (including infectious causes) and remedy these causes if possible (e.g. discontinuation of concomitant medication, dietary modification, treatment of comorbidity).

The patient should be monitored for signs of dehydration and instructed to take preventive measures against dehydration as soon as diarrhea occurs. Antidiarrheal medication must be initiated at the first sign of abdominal cramping, loose stools or overt diarrhea. Concomitant medication for the treatment of diarrhea should follow local practice and the investigator's best judgment and may follow "the recommended guidelines for the treatment of cancer treatment-induced diarrhea" ([Benson et al 2004](#)). For example:

- For uncomplicated diarrhea (grade 1 or 2 without complicating signs or symptoms), loperamide given at a standard dose (e.g. initial administration of 4 mg orally, then 2 mg every 2-4 hours, maximum of 16 mg/day), along with oral hydration, and dietetic measures should be considered. Note: complicating signs or symptoms include: moderate to severe cramping, decreased performance status, fever, neutropenia, frank bleeding or dehydration.
- For complicated diarrhea (all grade 3 or 4, grade 1-2 with complicating signs or symptoms), management should involve intravenous (IV) fluids, and consider treatment with octreotide (at starting dose of 100 to 150 μ g SC tid or 25 to 50 μ g IV) and antibiotics (e.g. fluoroquinolone) should be given.

Dose adaptation of LDK378 in case of treatment related diarrhea must follow the guidelines presented above in [Table 6-3](#).

6.3.4.7 Guidelines for treatment of hypophosphatemia

In the phase I study [CLDK378X2101], as of 31-Oct-2013, there were 9 cases of grade 3 hypophosphatemia in all dose groups, one of which was a DLT that contributed to the MTD determination – this patient was able to continue LDK378 at the same dose. One patient in the 750 mg group had a grade 3 hypophosphatemia that resolved after dose adjustment or interruption; in the remaining 8 cases, patients were able to continue therapy without dose modification. Hypophosphatemia was a commonly reported AE (6.3%), regardless of relationship to LDK378 treatment. Therefore, phosphate levels will be checked at baseline and during treatment. In cases of hypophosphatemia at baseline, phosphate supplements should be started before treatment with LDK378. For any grade of hypophosphatemia during the study, treatment with phosphate supplements should be given as clinically indicated, and the LDK378 dose can be maintained.

6.3.4.8 Guidelines for the follow-up of laboratory pancreatic abnormalities

In case of any occurrence of lipase or amylase increase to grade 3 or 4, both lipase and amylase must be monitored weekly (or more frequently if clinically indicated) until the event resolves to \leq grade 1 (or to baseline).

After resumption of dosing, monitoring must be continued weekly (or more frequently if clinically indicated) for one additional cycle (i.e. 4 weeks). If there is no recurrence of \geq grade 2 amylase or lipase elevations during this period, subsequent monitoring must be performed every 4 weeks.

Patients who discontinue study treatment due to pancreatic toxicity must be monitored weekly (or more frequently if clinically indicated) until the event resolves to \leq grade 1 or stabilization occurs (no CTCAE grade change over 4 weeks). Refer to [Table 6-4](#).

If amylase and/or lipase elevations are accompanied by new or progressive unexplained abdominal symptoms such as severe pain or vomiting, withhold LDK378, then perform diagnostic procedures (e.g., abdominal CT scan or ultrasound) to exclude pancreatic pathology.

See also dose modification guidelines described in [Table 6-3](#).

Table 6-4 Follow-up evaluations for selected toxicities

Toxicity	Follow-up evaluation*
Investigations (hematologic)	Febrile neutropenia, neutropenia or thrombocytopenia \geq CTCAE Grade 3 Test weekly (or more frequently) until \leq Grade 2 Subsequent monitoring must be performed every 4 weeks
Investigations (hepatic)	Total bilirubin/ALT/AST Grade 2: (patients with liver metastasis and grade 2 AST/ALT at baseline, increased monitoring required for grade 3 ALT/AST). Follow guidelines for grade 3 or 4 AST/ALT Test weekly (or more frequently) until \leq Grade 1 Thereafter, continue to test every 2 weeks (or more frequently) for 8 weeks. If no recurrence of \geq Grade 2 event, continue monitoring every 4 weeks Total bilirubin/ALT/AST \geq Grade 3: Test weekly (or more frequently) until \leq Grade 1 Thereafter, continue to test every 2 weeks (or more frequently) for 16 weeks. If no recurrence of \geq Grade 2 event, continue monitoring every 4 weeks Discontinuation due to liver toxicity: Test weekly (or more frequently) until \leq Grade 1 or stabilization
Investigations (renal)	Serum creatinine Grade 2: Test weekly (or more frequently) until Grade 1 Thereafter, test every cycle (4 weeks) Serum creatinine \geq Grade 3: Test twice weekly (or more frequently) until \leq Grade 1 Thereafter, test every cycle (4 weeks)
Investigations (pancreatic)	Amylase/lipase \geq Grade 3: Test weekly (or more frequently) until \leq Grade 1. After resumption of dosing, continue to test weekly for one additional cycle (4 weeks). If no reoccurrence of \geq Grade 2 event, continue monitoring every cycle (4 weeks).

*Note: this table refers only to the evaluation schedule only. Refer to [Table 6-3](#) for dose modifications required for applicable toxicities

6.3.5 Anticipated risks and safety concerns of the study treatment

Appropriate eligibility criteria and specific dose modification and stopping rules are included in this protocol. Recommended guidelines for prophylactic or supportive treatment for expected toxicities, including management of study-drug induced AEs, e.g., diarrhea are provided in [Section 6.3.4](#). Refer to preclinical toxicity and or clinical data found in the Investigator's brochure (IB).

6.4 Concomitant medications

In general, the use of any concomitant medication/therapy deemed necessary for the care of the patient (e.g. such as anti-emetics, anti-diarrhea) is permitted (see [Section 6.4.1](#)), except when specifically prohibited (see [Section 6.4.2](#)).

The patient must be told to notify the investigational site about any new medications he/she takes after the start of the study drug. All medications including herbal/natural medications (excluding study treatment and prior antineoplastic treatments and blood transfusions), surgeries and procedures (including physical therapy) administered within 28 days prior to the

first dose of administration of LDK378 through 30 days after the last dose of LDK378 will be recorded in the Concomitant Medications or Surgical and Medical Procedures eCRF, respectively. Medications include not only physician prescribed medications, but also all over-the counter medications, herbal medications (prohibited, see [Section 6.4.2.7](#)), food and or vitamin supplements.

6.4.1 Permitted concomitant therapy

6.4.1.1 Corticosteroids

Chronic dosing of corticosteroids such as dexamethasone and prednisone is known to induce CYP3A enzymes, thereby increasing the risk of reducing LDK378 drug exposure to sub-therapeutic levels.

If possible, systemic corticosteroid treatment should not be given during the study, except for:

- Topical applications (e.g. rash), inhaled sprays (e.g. obstructive airways diseases), eye drops or local injections (e.g. intra-articular);
- Stable doses of corticosteroid therapy such as dexamethasone or prednisone (e.g., for tumor associated symptoms) are permitted during the course of the study. If increasing doses of corticosteroids are required during the study treatment, LDK378 must be held and the corticosteroid dose must have been stabilized (or decreasing) for at least 5 days before LDK378 is resumed.

6.4.1.2 Bisphosphonates

The use of bisphosphonates is allowed regardless of indication provided patients have been on stable doses optimally for at least 4 weeks prior to the start of treatment. Patients requiring initiation of bisphosphonate treatment during the course of the study should be evaluated for progressive disease and the result of the evaluation should be clearly documented in the patients' source documentation.

No drug-drug interaction is expected between LDK378 and bisphosphonates as the two drugs are eliminated through different elimination pathways. Bisphosphonates are not inhibitors of human CYP450 enzymes involved in the metabolism of LDK378 and do not undergo metabolism *in vivo*.

The same guidelines apply to the use of denosumab for the treatment of bone metastatic disease.

6.4.1.3 Drugs that are metabolized by CYP450 enzymes

In vitro drug metabolism studies show that the metabolism of LDK378 is mediated by CYP3A4/5. LDK378 is a time-dependent CYP3A4/5 inhibitor and is also a potent reversible inhibitor of CYP2A6, 2E1, 2C9 and 3A4/5 and may consequently increase exposure to drugs metabolized by these enzymes at clinically relevant concentrations. Clinical studies have not yet been performed to confirm the potential effect of LDK378 on substrate drugs metabolized by these enzymes in patients. The risk for CYP2A6 and CYP2E1 is largely mitigated by the low potential for drugs metabolized by these enzymes to be co-administered with LDK378.

Concomitant treatment of LDK378 with weak inhibitors or inducers of CYP3A4/5 is permitted. Caution is advised when LDK378 is co-administered with drugs that are moderate inhibitors or inducers of CYP3A4/5 ([Table 14-2](#) of Appendix 1). Duration of concomitant treatment should be kept as short as possible (e.g., less than 1 week), or completely avoided whenever possible. Patients receiving such medications must be monitored closely for any potentiation of toxicity or decrease of clinical benefit due to any individual concomitant medications, and may require dose titration or adjustment. Note that co-administration of LDK378 with strong inhibitors and inducers of CYP3A4/5 is prohibited (refer to [Section 6.4.2.5](#)).

Concomitant treatment of LDK378 with medications known to be metabolized by CYP2C9 and CYP3A4 is allowed with caution ([Table 14-2](#) of Appendix 1), except for drugs which have narrow therapeutic index/sensitive substrates for these CYP isoforms ([Section 6.4.2.6](#) and [Table 14-1](#) of Appendix 1).

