6.4.2.7 Herbal medications

Herbal preparations/medications are not allowed throughout the study, as a potential drug-drug interaction is always possible. These herbal medications include, but are not limited to: St. John's wort, Kava, ephedra (ma huang), gingko biloba, dehydroepiandrosterone (DHEA), yohimbe, saw palmetto, and ginseng.

Patients should stop using herbal medications at least 7 days prior to first dose of study treatment.

6.4.2.8 Medications that may prolong the QT interval or have a known risk of inducing Torsades de Pointes

LDK378 has potent activity on the hERG channel with an IC_{50} of 0.4 μ M. However there were no LDK378-related effects *in vivo* in monkeys at doses as high as 100 mg/kg (human equivalent dose [HED] of 1950 mg).

Serial ECGs were collected following a single dose and at steady-state to evaluate the effect of LDK378 on the QT interval in an open-label, dose-escalation, and expansion study ([CLDK378X2101]). A total of 304 patients were treated with LDK 378 doses ranging from 50 to 750 mg with 255 patients treated with LDK378 750 mg. One of 304 patients (<1%) was found to have a QTc >500 msec and 10 patients (3.3%) had an increase from baseline QTc >60 msec. A central tendency analysis of the QTc data at average steady-state concentrations demonstrated that the upper bound of the 2-sided 90% CI for QTc was 16 msec at LDK378 750 mg. A pharmacokinetic/pharmacodynamic analysis suggested concentration-dependent QTc interval prolongation.

Concomitant administration of LDK378 with drugs known to have a high risk of increasing the QTc interval, and drugs known to increase the QTc interval that are also primarily metabolized by CYP3A4/5 should be avoided. Concomitant use of LDK378 and any medication included in [Table 14-4](#) of Appendix 1 titled “List of prohibited QT prolonging drugs” (i.e., drugs that are generally accepted by the Qtdrugs.org Advisory Board of the Arizona CERT to have a known risk of causing Torsades de Pointes) is not permitted.

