* Compounds known to increase QTc interval that are also primarily metabolized by CYP3A4/5. For an updated list of CYP2C9 substrates, CYP3A substrates, inhibitors and inducers, please reference the Novartis Oncology Clinical Pharmacology internal memo: drug-drug interactions (DDI) database, Oct 2010, which is compiled primarily from the FDA's "Guidance for Industry, Drug Interaction Studies", the Indiana University School of Medicine's Drug Interactions Database, and the University of Washington's Drug Interaction Database.

**Sensitive substrates: Drugs that exhibit an AUC ratio (AUCi/AUC) of 5-fold or more when co-administered with a known potent inhibitor.

Substrates with narrow therapeutic index (NTI): Drugs whose exposure-response indicates that increases in their exposure levels by the concomitant use of potent inhibitors may lead to serious safety concerns (e.g., Torsades de Pointes).

Table 14-2 List of medications to be used with caution

CYP2C9 substrates			
losartan	irbesartan	diclofenac	ibuprofen
piroxicam	tolbutamide	glipizide	acenocoumarol
celecoxib	sulfamethoxazole	tolbutamide	torsemide
CYP3A4/5 substrates			
dronedarone	capravirine	aripiprazole	casopitant
alprazolam	ritonavir	haloperidol	quinine
diazepam	telaprevir	imatinib	tamoxifen
amlodipine	atorvastatin	nilotinib	tolvaptan
diltiazem	everolimus	methadone	trazodone
nifedipine	erythromycin	boceprevir	vincristine
nisoldipine		brecanavir	verapamil
nitrendipine			
Moderate CYP3A4/5 inhibitors			
ciprofloxacin	darunavir	grapefruit juice	dronedarone
erythromycin	fosamprenavir	aprepitant	tofisopam
amprenavir	diltiazem	casopitant	
atazanavir	verapamil	cimetidine	
Moderate CYP3A4/5 inducers			
bosentan	efavirenz	etravirine	modafinil
nafcillin	ritonavir	talviraline	tipranavir
Proton pump inhibitors			
esomeprazole	lansoprazole	omeprazole	pantoprazole
rabeprazole			

The list of CYP2C9 and 3A4/5 substrates, 3A4/5 inhibitors and inducers is from the Novartis Oncology Clinical Pharmacology internal memo: drug-drug interactions (DDI) database, Oct 2010, which is compiled primarily from the Indiana University School of Medicine's "Clinically Relevant" Table (medicine.iupui.edu/flockhart/table.htm), the University of Washington's Drug Interaction Database (druginteractioninfo.org), and the FDA's "Guidance for Industry, Drug Interaction Studies".

Table 14-3 List of prohibited enzyme-inducing anti-epileptic drugs

Prohibited enzyme-inducing anti-epileptic drugs			

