carbamazepine	ethotoin	felbamate	fosphenytoin
phenobarbital	phenytoin	primidone	topiramate

Table 14-4 List of prohibited QT prolonging drugs**Prohibited medications causing QTc prolongation**

Antiarrhythmic:	Anticancer:	Antibiotic:	Antiangular:
amiodarone	arsenic trioxide	azithromycin	bepridil
disopyramide	vandetanib	clarithromycin*	Antipsychotic:
dofetilide	Antihistamine:	erythromycin*	chlorpromazine
flecainide	astemizole*	moxifloxacin	haloperidol*
ibutilide	terfenadine*	sparfloxacin	mesoridazine
procainamide	Antimalarial:	levofloxacin	pimozide
quinidine*	chloroquine	Antinausea:	thioridazine
sotalol	halofantrine	domperidone	sulpiride
Antilipemic:	Anti-infective:	droperidol	Opiate agonist:
probucol	pentamidine	ondansetron	levomethadyl
		GI stimulant:	methadone
		cisapride*	cocaine
			Other:
			anagrelide
			sevoflurane
Antidepressant:			
citalopram			

Please note: *CYP3A substrate Source: Arizona Center for Education and Research on Therapeutics (CERT), Drugs that prolong the QT interval and/or induce Torsades de Pointes, <http://azcert.org/medical-pros/drug-lists/drug-lists.cfm>

15 Appendices

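### Table 14-2 lists erythromycin, haloperidol and methadone as caution-only drugs, but Section 6.4.2.8 and Table 14-4 prohibit them as QT-prolonging

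*Protocol*

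**What the plan says.** Section 6.4.1.3 of the protocol gives two permissions that both rely on Table 14-2 in Appendix 1, whose title is "List of medications to be used with caution".

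- **Substrates:** "Concomitant treatment of LDK378 with medications known to be metabolized by CYP2C9 and CYP3A4 is allowed with caution", "except for drugs which have narrow therapeutic index/sensitive substrates for these CYP isoforms". The exception cites Section 6.4.2.6 and Table 14-1.
- **Moderate inhibitors and inducers:** "Caution is advised when LDK378 is co-administered with drugs that are moderate inhibitors or inducers of CYP3A4/5". Use is to be kept short or avoided.

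The same section adds one reminder of a ban: "Note that co-administration of LDK378 with strong inhibitors and inducers of CYP3A4/5 is prohibited". It does not mention QT-prolonging drugs.

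Section 6.4.2.8 deals with those. It says that "drugs known to increase the QTc interval that are also primarily metabolized by CYP3A4/5 should be avoided", and it does not permit any drug in Table 14-4. The heading inside that table is "Prohibited medications causing QTc prolongation", and its footnote explains the asterisk on some names: "Please note: *CYP3A substrate".

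**The concern.** The same appendix gives opposite instructions for the same drugs. Someone checking a new prescription for a CYP3A4 substrate would go to Section 6.4.1.3, then to Table 14-2, and find erythromycin, haloperidol and methadone marked as usable with caution. Nothing in Section 6.4.1.3 or in the note under Table 14-2 sends that reader on to Section 6.4.2.8 or Table 14-4.

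The consequence concerns safety and conduct. Section 6.4.1.3 warns that LDK378 may raise exposure to CYP3A4/5 substrates, Section 6.4.2.8 describes a concentration-dependent QTc effect of LDK378, and QT prolongation is an adverse event of special interest in Section 8.1.3. Section 7.1.3 lists use of an Appendix 1 prohibited treatment among the circumstances in which study treatment must be discontinued, and SAP Section 2.6 counts it as a protocol deviation. A site could therefore trigger a mandatory stop by following the protocol's own caution table.

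**Working it through.** The plan has no figure to reproduce. The check is a name-by-name match of Table 14-2 against the three prohibition tables in Appendix 1.

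**Inputs**

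- Table 14-2, by block: 12 CYP2C9 substrates + 28 CYP3A4/5 substrates + 14 moderate inhibitors + 8 moderate inducers + 5 proton pump inhibitors = 67 entries. Seven names occur twice (tolbutamide, dronedarone, casopitant, ritonavir, diltiazem, erythromycin, verapamil), so there are 67 − 7 = 60 distinct items.
- Table 14-4: 39 drugs, of which 7 carry the CYP3A-substrate asterisk.

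**Step 1: Table 14-2 against Table 14-4 (QT-prolonging drugs)**

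| Drug | Block in Table 14-2 | Table 14-4 | Table 14-1 |
|---|---|---|---|
| Erythromycin | CYP3A4/5 substrates; moderate inhibitors | Prohibited, asterisked | Absent |
| Haloperidol | CYP3A4/5 substrates | Prohibited, asterisked | Absent |
| Methadone | CYP3A4/5 substrates | Prohibited, no asterisk | Absent |

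The overlap is exactly three drugs and 2 + 1 + 1 = 4 entries. Three of the four fall under the substrate permission. The fourth, erythromycin as a moderate inhibitor, falls under the stricter caution sentence, which still allows use. Since none of the three is in Table 14-1, the exception in Section 6.4.1.3 does not reach them.

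**Step 2: the asterisked drugs in Table 14-4**

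The seven are astemizole, cisapride, clarithromycin, erythromycin, haloperidol, quinidine and terfenadine. Five of them (astemizole, cisapride, clarithromycin, quinidine, terfenadine) are in Table 14-1 and not in Table 14-2, so they are handled consistently. The other 7 − 5 = 2, erythromycin and haloperidol, are in Table 14-2 and not in Table 14-1. Table 14-4 thus itself identifies as CYP3A substrates two of the drugs that Table 14-2 releases with caution.

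**Step 3: Table 14-2 against Table 14-1**

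Ritonavir (CYP3A4/5 substrates and moderate inducers, 2 entries) and tipranavir (moderate inducers, 1 entry) are prohibited in Table 14-1 as strong CYP3A4/5 inhibitors. That is 3 entries. Section 6.4.1.3 repeats the ban on strong inhibitors, so here only the table is wrong.

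**Step 4: Table 14-2 against Table 14-3 (enzyme-inducing anti-epileptics)**

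No overlap.

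**Total:** 4 + 3 = 7 of 67 entries, and 3 + 2 = 5 drugs.

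**The case against.** The strongest answer is that the protocol already says which rule wins. The opening of Section 6.4 makes permitted therapy subject to the specific prohibitions in Section 6.4.2, and Section 6.4.1.3 sits under that rule. Exclusion criterion 12 also bars QT-risk drugs for the duration of the study. On this view Table 14-2 is a CYP classification list drawn from an interaction database, and a section on CYP metabolism need not repeat the QT rule. Safeguards exist too: Table 7-5 schedules an ECG in every cycle, and the Grade 3 QTcF rule in Table 6-3 includes a review of concomitant medication.

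Most of this is right, and it is why the point is minor. It settles which instruction should prevail. It does not make Table 14-2 correct, because the table's title and Section 6.4.1.3 both use it as prescribing guidance. Section 6.4.1.3 does restate some prohibitions, so silence on QT drugs can be read as permission. The ECG and QTcF rules act only after exposure.

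A second objection is that the count is incomplete. Acenocoumarol is in Table 14-2 while Section 6.4.2.3 bars coumarin derivatives, and several anticancer agents in Table 14-2 would be barred by Section 6.4.2.1 if given as anticancer therapy. The seven entries are a match of table against table and do not cover these. The documents do not state acenocoumarol's class, and the ban on the anticancer agents depends on how they are used. Neither changes the result for the five drugs named.

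**Conclusion.** The concern holds as an internal inconsistency of minor severity. Three drugs prohibited for QT prolongation appear in four entries of a caution-only table, and the exception in Section 6.4.1.3 does not exclude them. Ritonavir and tipranavir add three entries as a secondary list error.

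The conclusion rests only on the current text of Section 6.4.1.3, Section 6.4.2.8 and Appendix 1, with no outside drug information. The documents give no rate of use for these drugs, so no number of affected patients can be stated. The response rate, its confidence interval and the sample-size reasoning are untouched.

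**What to change.** In the next amendment:

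1. Delete seven entries from Table 14-2: erythromycin (CYP3A4/5 substrates and moderate inhibitors), haloperidol and methadone (CYP3A4/5 substrates), ritonavir (CYP3A4/5 substrates and moderate inducers) and tipranavir (moderate inducers).
2. At the end of Section 6.4.1.3, extend the exception so that, besides Section 6.4.2.6 and Table 14-1, it also covers QT-prolonging drugs under Section 6.4.2.8 and Table 14-4.

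Section 6.4.2.8 and Table 14-4 stay as they are. While Table 14-2 is open, the sponsor should also check acenocoumarol against Section 6.4.2.3. The cost is seven deletions and one cross-reference, with no new procedure and no change to the analysis.
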